1.0 OBJECTIVES AND SCIENTIFIC AIMS

Primary Objectives: In patients with high anxiety undergoing THA or TKA:

- 1) Determine if preoperative acupuncture reduces preoperative anxiety in the acupuncture group.
- 2) Examine postoperative pain following acupuncture compared to control.

Secondary Objective: To determine the safety of preoperative acupuncture by recording complications throughout hospital length of stay; to determine whether preoperative acupuncture reduces postoperative nausea and vomiting, reduces postoperative opioid consumption, reduces anxiolytics need during hospitalization and improves satisfaction compared to control in high-anxiety patients undergoing THA or TKA.

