7.0 INTERVENTION ORDER OF EVENTS

7.1 Acupuncture Group

1. On the day of surgery and prior to procedure, study patients will be waiting in the preoperative area.
2. The patient will be placed in bay #1 or other bay if #1 is not available in the preoperative area.
3. A member of the study personnel will assess the patient's baseline anxiety and pain.
4. The assigned acupuncturist will conduct a preoperative medical assessment and chart review on the patient prior to intervention.
5. The patient will then undergo the acupuncture procedure given by the assigned acupuncturist.
6. Anxiety and pain will be reassessed by a member of the study personnel after the procedure.
7. The patient will undergo their surgical procedure.
8. The patient will be reevaluated for pain three times; when they arrive to the post-anesthesia recovery unit (PACU), after an hour, and after 3 hours.
9. The patient will be reevaluated for PONV/Impact score two times; after an hour from their arrival to the post-anesthesia recovery unit (PACU), and after 3 hours. Postoperative antiemetics used will also be collected from the patient's chart retrospectively, following enrollment.
10. Postoperative opioid consumption and anxiolytics used throughout hospitalization will be collected from the patient's chart retrospectively, following enrollment.
11. Admission and discharge dates & times will be collected directly from the patient's chart retrospectively, following enrollment and used to determine total hospital length of stay.
12. Patient satisfaction regarding surgery will be evaluated within a week after the discharge from the hospital.

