7.2 Control Group

1. On the day of surgery and prior to procedure, study patients will be waiting in the preoperative area.
2. The patient will be placed in bay #1 or other bay if #1 is not available in the preoperative area.
3. A member of the study personnel will assess the patient's baseline anxiety and pain.
4. The patient will undergo their surgical procedure.
5. The patient will be reevaluated for pain three times; when they arrive to the post-anesthesia recovery unit (PACU), after an hour, and after three hours.
6. The patient will be reevaluated for PONV/Impact score two times; after an hour from their arrival to the post-anesthesia recovery unit (PACU), and after 3 hours. Postoperative antiemetics used will also be collected from

- the patient's chart retrospectively, following enrollment.
7. Postoperative opioid consumption and anxiolytics used throughout hospitalization will be collected from the patient's chart retrospectively, following enrollment.
 8. Admission and discharge dates & times will be collected directly from the patient's chart retrospectively, following enrollment and used to determine total hospital length of stay.
 9. Patient satisfaction regarding surgery will be evaluated within a week after the discharge from the hospital.

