PostOP	PACU: on arrival, 1 hour, and 3 hours	
 • Pain/NPS • Anxiolytics 	
 • Pain/NPS • Anxiolytics
PostOP	PACU: 1 hour, and 3 hours after arrival	
 • PONV/impact score 	
 • PONV/impact score
PO-Discharge	chart review	
 • Opioid use/MME • Anxiolytics • Antiemetics • Hospital length of stay 	
 • Opioid use/MME • Anxiolytics • Antiemetics • Hospital length of stay
Within a week from discharge	Phone call	
 • Satisfaction questionnaires 	
 • Satisfaction questionnaires

Abbreviations: NPS, numeric pain rating scale; PACU, post-anesthesia care unit; PONV, postoperative nausea and vomiting; POD, postoperative day.

Figure 3. Protocol schema.

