For the primary aim *pain*, based on data from the first 31 patients enrolled, our sample size calculation indicates that a minimum of 26 subjects per group are needed using a repeated measures design (each subject is measured 4 times) with 2 groups for a total of 52 subjects. This design achieves 81% power to test factor B1 if a Geisser-Greenhouse Corrected F Test is used with a 5% significance level and the actual effect standard deviation is 0.255 (an effect size of 0.40319). We estimate an attrition rate of 10%, which will require 58 subjects; however we will aim to enroll 60 subjects (30 per group). For the second primary aim *anxiety*, we performed two sample size calculations. One based on the data of all 17 patients in the acupuncture group, and another excluding the 3 patients for which protocol deviations were reported due to methods collecting the anxiety measure. With all 17 patients, the difference in the response of anxiety from pre to post acupuncture was normally distributed with a standard deviation 26.27. If the true difference in the mean response of matched pairs is 35.64, we will need to study 6 pairs of subjects to be able to reject the null hypothesis that this response difference is zero with probability (power) 0.8. The Type I error probability associated with this test of this null hypothesis is 0.05. With the 3 patients removed, the difference in the response of anxiety from pre to post acupuncture was normally distributed with standard deviation 26.588. If the true difference in the mean response of matched pairs is 39.14, we will need to study 6 pairs of subjects to be able to reject the null hypothesis that this response difference is zero with probability (power) 0.8. The Type I error probability associated with this test of this null hypothesis is 0.05.

Pain is the more appropriate primary outcome of the two primary outcomes to base the sample size on because there are 4 time points of data for each group for this variable. The other primary outcome, *anxiety* does not have a post measure for the control group (per the study design), and therefore a within-group pre to post change in the acupuncture group is being performed to examine this outcome. We acknowledge that this within group design is weaker than the design to assess the pain outcome measure.

Statistical Methods

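### The re-estimated pain sample size fits a group effect averaged over four ratings, at least one pre-operative, so its 81% is not power for postoperative pain; the mixed model names no responses, contrast or baseline role

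*Combined protocol and SAP*

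**What the plan says.** The second primary objective (section 1.0) is to "Examine postoperative pain following acupuncture compared to control".

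Sections 7.1, 7.2 and 8.0 (Table 1) schedule these pain ratings:

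| Rating | Acupuncture | Control |
|---|---|---|
| Holding bay, before acupuncture | yes | yes |
| Holding bay, after acupuncture | yes | not applicable |
| PACU arrival, 1 h, 3 h | yes | yes |

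The postoperative row of Table 1 reads "PACU: on arrival, 1 hour, and 3 hours". The extra acupuncture-arm rating comes from section 7.1: "Anxiety and pain will be reassessed by a member of the study personnel after the procedure".

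The re-estimate in section 11.0 uses the first 31 patients and finds that "a minimum of 26 subjects per group are needed using a repeated measures design (each subject is measured 4 times) with 2 groups". It continues: "This design achieves 81% power to test factor B1 if a Geisser-Greenhouse Corrected F Test is used", at the 5% level, with effect standard deviation 0.255 and effect size 0.40319. Pain is preferred for sizing because "there are 4 time points of data for each group for this variable". The four are not listed, and factor B1 is not defined.

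Statistical Methods gives two analyses. The first is a two-group test at each time point. The second is a mixed model for repeated outcomes such as pain. For that model the plan gives no list of response times, no contrast and no role for baseline pain, and it leaves time as either categorical or numeric.

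**The concern.** A rating taken before needling cannot respond to needling. If such a rating is averaged with the postoperative ones, the group effect is diluted and noise is added. The quantity that was sized is then not the quantity in the objective.

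The mixed model does not settle the matter. A reader cannot tell whether its group term, a group-by-time term or a postoperative contrast is the answer for pain, or whether baseline pain is a response, a covariate or unused. Pain data from 31 open-label patients have already been used, so these choices should be closed before the final analysis.

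**Working it through.** **1. Reproduce the plan's figure.** For a between-group main effect on each patient's mean rating, λ = N f² = 52 × 0.40319² = 8.45, with 1 and 50 degrees of freedom and two-sided α = 0.05. Power is 0.814 at N = 52 and 0.798 at N = 50, so 26 per group is the smallest size reaching 80%. Attrition: 52/0.9 = 57.8, rounded up to 58. Time or interaction tests with 3 numerator degrees of freedom give 0.67 (λ = N f²) or 0.999 (λ = 4N f²); neither matches 81%.

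**2. Implied quantities.** Group difference in the four-rating mean: 2 × 0.255 = 0.51. SD of that mean: 0.255/0.40319 = 0.632 (variance 0.400).

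**3. Which ratings.** Control has four pain ratings in all, so its four must be the holding-bay baseline plus three in PACU. The acupuncture arm has five, and the plan does not say which four were used. Table 1 favours the pre-acupuncture rating, the only pre-operative time filled in both arms.

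**4. Efficiency.** Let D be the average PACU difference, with no true baseline difference. The four-rating mean shows (0 + 3D)/4 = 0.75D. The sums of four and of three ratings both carry 3D, so the ratio of required N is Var(sum of 4)/Var(sum of 3). This exceeds 1 whenever the baseline-PACU correlations are non-negative. With equal variances, baseline-PACU correlation a and PACU-PACU correlation b, it equals (4 + 6a + 6b)/(3 + 6b):
- a = b = 0: 4/3 = 1.33
- a = b = 0.2: 6.4/4.2 = 1.52
- a = b = 0.5: 10/6 = 1.67
- baseline variance a quarter of PACU variance, a = 0, b = 0.5: 6.25/6 = 1.04

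**5. Power at N = 52.** The documents give no correlation, so r = 0 / 0.2 / 0.5 with compound symmetry is assumed. Holding the four-rating variance at 0.400, the single-rating variance is σ² = 1.6/(1 + 3r), so σ = 1.265 / 1.000 / 0.800. The variance of the three-PACU mean is σ²(1 + 2r)/3, or σ²[(1 + 2r)/3 − r²] with baseline as covariate. λ = N D²/(4 × variance).

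For the last two rows, control patients at the interim number 31 − 17 = 14, since the anxiety calculation was "One based on the data of all 17 patients in the acupuncture group". The standard error (SE) of an interim baseline difference is σ√(1/17 + 1/14) = 0.457 / 0.361 / 0.289. If a chance difference of k SE contributed to the 0.51, then D = (4 × 0.51 − k SE)/3.

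| Scenario | D | Four-rating effect | Three-PACU | Three-PACU, covariate |
|---|---|---|---|---|
| 0.51 is the four-rating difference, no interim baseline difference | 0.51/0.75 = 0.68 | 81% | 91 / 94 / 96% | 91 / 96 / 99.6% |
| 0.51 is the postoperative difference | 0.51 | 57% | 69 / 75 / 79% | 69 / 79 / 94% |
| Interim baseline difference of 1 SE contributed | 0.528 / 0.560 / 0.584 | 60 / 65 / 69% | 72 / 83 / 88% | 72 / 86 / 98% |
| Interim baseline difference of 2 SE contributed | 0.376 / 0.439 / 0.488 | 35 / 45 / 53% | 44 / 62 / 75% | 44 / 66 / 92% |

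The four-rating column assumes the pre-acupuncture rating and a true baseline difference of zero (difference tested 0.75D). A chance difference of 1 SE in the other direction would raise three-PACU power to 98 / 98 / 99%.

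**6. Error rate.** In simulation (8,000 trials per setting), type I error was 0.048 to 0.054 for the four-rating, three-PACU and covariate-adjusted tests.

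**The case against.** **The four-rating test is not actually planned.** Statistical Methods chooses a mixed model over repeated-measures ANOVA, and a model with categorical time could give a postoperative contrast. It also expects measurement times to vary because they are taken after surgery, which hints at postoperative responses. This stands: the efficiency loss is conditional on the four-rating effect being the one tested. But if the model uses only PACU ratings, the 81% still belongs to a different quantity.

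**The tests at each time point address postoperative pain directly.** True, and they are unaffected. They are several tests, none is named as deciding the objective, and the re-estimate does not power them.

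**The original sample size tables cover postoperative pain.** They do, but at other time points and from an earlier study, which is the plan's own reason for re-estimating.

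**The reading of factor B1 is inferred.** Yes. It rests on the arithmetic, because the documents do not define the term.

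**The ratios depend on assumed variances and correlations.** Yes. Only the direction is general, for non-negative baseline-PACU correlation; the size can fall to about 1.04 or closer to 1.

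**Baseline pain may not be on one scale.** Table 1 lists the holding-bay rating as VAS for control and NPS for acupuncture, while the outcome list in section 8.0 gives NPS for pain. This may be a slip, but the documents do not settle it, and it limits use of that rating as a covariate.

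**Conclusion.** The point holds in two parts. First, the stated 81% is not power for the postoperative pain objective: it fits a group effect over four ratings, of which at most three are postoperative. Second, the mixed model leaves its responses, contrast and baseline role open.

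If the four-rating effect is tested with no true baseline difference, the cost is a factor of 1.33 to 1.67 in patients under the assumed compound symmetry, and possibly close to none if baseline variance is small and its correlation with PACU pain is near zero. The three-PACU contrast had the higher power in every scenario computed.

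Two stronger readings are not supported:
- A reader might infer that 52 patients are enough for a postoperative contrast, or that they are too few. The documents settle neither. Unadjusted power is 91 to 96%, 69 to 79%, or as low as 44%, depending on interim means by time that are not reported.
- A reader might infer bias or a raised false-positive rate. Neither follows; the issue is efficiency, fit to the objective and missing specification.

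**What to change.** Amend section 11.0, dated before the final analysis, in this order:

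1. Reconcile the VAS and NPS entries for holding-bay pain in Table 1, and state which scale was recorded in each arm.
2. State that the mixed-model response for pain is the rating at PACU arrival, 1 h and 3 h, with time categorical, and that the primary contrast is the group difference averaged over those three times.
3. State that the pre-acupuncture holding-bay rating, taken in both groups, is the baseline covariate, provided it was recorded on one scale. Otherwise use the same contrast without it.
4. State which acupuncture-arm ratings entered the 52-patient calculation.
5. Restate power for the new contrast at the planned 60 patients (54 after 10% attrition), with the SD and between-rating correlation used, whether it rises or falls.

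The cost is one amendment with its IRB submission and one re-run on data already held. The restated power may be less favourable than 81%; no increase in enrolment is requested.

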Patient demographic and clinical (including operative) characteristics will be compared between groups using an independent samples t-test if continuous data are normally distributed), or Mann Whitney U if continuous data are not normally distributed. A chi-square or Fisher's exact test (if cell counts are <5) will be used to compare these characteristics between groups for categorical variables. All continuous variables will be expressed as mean±SD or median, IQR as appropriate. Categorical variables will be expressed as frequency (%).

The primary and secondary study outcomes will be compared between groups two ways. First, an independent samples t-test or Mann Whitney U test if deemed more appropriate for the scale data (which may be considered ordinal) will be used to compare outcomes at each time point between the two groups. Second, a mixed model for repeated measures will be used to compare the study outcomes that are repeated over time (e.g., Pain). This model was chosen instead of a repeated measures ANOVA due to the ordinal nature of the repeated outcome measures in addition to this test being more appropriate for non-normal residuals, missing data, as well as the ability to treat the time points as discrete categories or as true numbers, which accounts for any variability in when the measures are administered to patients.

We anticipate that the timing of the measures being administered may fluctuate slightly due to measures being taken PostOP.

All analyses will be conducted using SPSS version 26.0. P (2-sided) < .05 will be deemed the level of statistical significance.

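### Pain and anxiety are both primary at 0.05 with no rule linking them, so the plan permits a positive primary claim on the uncontrolled anxiety test alone, a test the interim figures already nearly settle

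*Combined protocol and SAP*

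**What the plan says.** Section 1.0 lists two objectives under one primary heading. The first is "Determine if preoperative acupuncture reduces preoperative anxiety in the acupuncture group". The second is "Examine postoperative pain following acupuncture compared to control".

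Section 11.0 (Sample Size) sizes each separately at the full 5% level. For pain, a "Geisser-Greenhouse Corrected F Test is used with a 5% significance level". For anxiety, "The Type I error probability associated with this test of this null hypothesis is 0.05". It explains that controls have no second anxiety measurement, so "a within-group pre to post change in the acupuncture group is being performed to examine this outcome", and it concedes that this design is the weaker of the two. On choosing between them it says only: "Pain is the more appropriate primary outcome of the two primary outcomes to base the sample size on".

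Section 11.0 (Statistical Methods) then sets one threshold for everything: "P (2-sided) < .05 will be deemed the level of statistical significance". It describes between-group comparisons of the primary and secondary outcomes and names no paired test for anxiety. Neither section gives a testing order, a division of alpha, or a statement of what combination of results counts as success.

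**The concern.** Two primary tests at 0.05 each, with no rule joining them, leave the headline conclusion open until the results are known. If anxiety is significant and pain is not, a report could say that a primary outcome was met, and nothing in the plan would contradict it.

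The two tests also differ in kind. Pain is the only primary that uses the control arm. The anxiety test asks whether scores change from before to after the session, with no concurrent comparison. Its interim mean and SD are printed in the plan, so its likely result was visible before enrolment ended. The randomised comparison could show nothing and the trial could still be presented as positive on a primary outcome.

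**Working it through.** **Inputs** (all from Section 11.0)
- Pain: effect size f = 0.40319; 26 per group (N = 52) for 81% power; 10% attrition; 60 to be enrolled (30 per group).
- Anxiety, all 17 acupuncture patients: mean change 35.64, SD 26.27.
- Anxiety, without the 3 patients with deviations (n = 14): mean change 39.14, SD 26.588.
- Alpha: two-sided 0.05 for each.

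Two assumptions are needed. The means are introduced as hypothetical true differences; they are taken here as the interim results because the calculations are said to rest on those patients' data. The test is taken to be a paired t-test because the calculation is for matched pairs. The plan does not say which patient set carries forward, so both are run.

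**1. The plan's own figures**
- Pain: between-group F test on 1 and 50 df, noncentrality N·f² = 52 × 0.40319² = 8.45. Power is 81.4%, against 81% stated. Attrition: 52/0.9 = 57.8, so 58, as stated.
- Anxiety: "If the true difference in the mean response of matched pairs is 35.64, we will need to study 6 pairs of subjects". The standardised change is 35.64/26.27 = 1.357; noncentral-t power is 75.7% at 6 pairs and 84.6% at 7. For the 14-patient set, 39.14/26.588 = 1.472 and power at 6 pairs is 81.9%. The stated 6 is reproduced to within one pair.

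**2. Cost of the missing rule when both nulls are true**
- Independent tests: 1 − 0.95² = 0.0975.
- Upper bound under any dependence: 0.05 + 0.05 = 0.10.

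**3. Where anxiety stands at the interim**

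| Set | t = mean/(SD/√n) | p | 95% CI for mean change |
|---|---|---|---|
| 17 patients | 35.64/(26.27/√17) = 5.59, 16 df | 0.00004 | 22.1 to 49.1 |
| 14 patients | 39.14/(26.588/√14) = 5.51, 13 df | 0.0001 | 23.8 to 54.5 |

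**4. What that implies for the final anxiety test**
- Power at the interim effect exceeds 99.99% at 26, 27 and 30 pairs in both sets.
- With 30 pairs, a mean change of about 9.8 (17-patient SD) or 9.9 (14-patient SD) is enough for p < 0.05.
- With the true change at the lower 95% limit, power at 30 pairs is 99.4% or 99.7%.
- Predictive probability of final significance, given the interim data, is about 0.9999 (17 patients) or 0.9996 (14 patients) for 26 to 30 pairs.
- If every remaining patient had a true mean change of zero, the 30-pair test would still be significant with probability 98% or 91%. If later patients became more anxious by 20 points on average, that falls to 26% or 5%.

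**5. Would splitting alpha help?** At 0.025 each:

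| Evaluable N | Pain power at 0.05 | Pain power at 0.025 |
|---|---|---|
| 52 | 81.4% | 72.3% |
| 60 | 86.7% | 79.2% |

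Reaching 80% for pain at 0.025 would take 31 per group: 62 evaluable, or 62/0.9 = 68.9, so 69 enrolled. The interim anxiety p-values (0.00004 and 0.0001) are already far below 0.025, so a split costs pain power and leaves anxiety significant.

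**The case against.** The best defence is that the plan asks two different questions, one within the acupuncture arm and one against control, and nowhere says that either answer makes the trial positive. It sizes the trial on pain, labels anxiety the second primary aim, and admits that the anxiety design is weaker. If both outcomes were required, pain would decide. Whether two distinct questions need a joint error rate is partly a matter of judgement.

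Much of this stands, and it rules out several stronger readings that a reader might infer:
- **That the trial cannot fail.** This needs an either-outcome rule. The plan permits that reading but does not adopt it.
- **That the chance of a false-positive primary is near 100%.** The figure above 99.99% is power at the interim effect. If anxiety does fall after the session, rejecting zero change is correct. It misleads only if read as acupuncture against control, and that is the separate problem of the missing control measurement. The error-rate cost of the missing rule is the 9.75%.
- **That anxiety is certain to be significant.** Practically certain is the most that can be said; the result would reverse if later patients worsened markedly.
- **That pain loses a gatekeeping role.** The plan never gives it one.
- **That the interim was a hypothesis test.** Section 11.0 says its sole purpose was re-estimation. The printed mean, SD and n nevertheless fix the t statistic once taken as the observed results.

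The defence does not close the gap. Preferring pain as the basis for sample size gives it no precedence in testing, Section 1.0 lists anxiety first, and Section 11.0 still calls anxiety a primary outcome.

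**Conclusion.** The point holds as a missing decision rule. Two primaries at 0.05 each, with neither order nor success criterion, allow a positive primary claim from the uncontrolled anxiety test alone. The general cost is a family-wise error of about 9.75%, assuming independent tests and two true nulls.

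The practical cost in this trial is that one significant primary is all but settled whatever the randomised pain comparison shows. That rests on reading the printed means and SDs as observed results, on a paired t-test, and on later patients not becoming more anxious on average. The conclusion is the same for both patient sets and from 26 to 30 pairs. The between-group pain analysis itself is not invalidated. This is a cheap improvement worth making.

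**What to change.** In Sections 1.0 and 11.0, state a fixed order: pain first at two-sided 0.05, then the within-arm anxiety change at 0.05 only if pain is significant. Alternatively, make pain the sole primary outcome and list anxiety as secondary. Either choice fits the plan's own view that the anxiety design is weaker. Do not split alpha, for the reasons shown in step 5.

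The interim, on the first 31 patients of an open-label trial, has already looked at both outcomes. The rule should therefore be introduced by a dated, IRB-approved amendment that says it was set after that look. The change works against the outcome that looks favourable, but it must still be disclosed.

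The cost is wording and the amendment process: no extra patients and no loss of pain power. The downside is that the anxiety result could no longer support a primary claim by itself.
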